**Table 4: Volume of Blood to be Collected From Each Participant**

Type of Sample	Volume per Sample (mL)	Number of Samples per Participant	Approximate Total Volume of Blood (mL) a
Safety (including screening and posttreatment assessments)			
- Hematology	2 d	9-12	18-24
- Serum chemistry b	2.5	9-12	22.5-30
Serology (HIV, hepatitis)	7.5	1	7.5
Serum $\beta$ -hCG pregnancy tests (for women of child-bearing potential only)	1	2	2
Pharmacokinetic samples	2	10-26	20-52
Approximate Total c			68-115.5

a. Calculated as number of samples multiplied by amount of blood per sample.

b. Serum chemistry excludes serology (HIV, hepatitis) and serum  $\beta$ -hCG pregnancy tests.

c. Repeat or unscheduled samples may be taken for safety reasons or technical issues with the samples.

d. Depending on local laboratory.

Key:  $\beta$ -hCG=beta human chorionic gonadotropin; HIV=human immunodeficiency virus

### Sample Collection and Handling

The actual dates and times of sample collection must be recorded in the eCRF or laboratory requisition form.

Refer to the Section 1.3, [Schedule of Activities \(SoA\)](#) for the timing and frequency of all sample collections.

Instructions for the collection, handling, storage, and shipment of samples are found in the laboratory manual that will be provided. Collection, handling, storage, and shipment of samples must be under the specified, and where applicable, controlled temperature conditions as indicated in the laboratory manual. Procedures for the collection, handling, and shipment of microbiological samples (sputum), as well as disclosure of blinded data are described in the Procedure for Confirmation and Reporting of Results of Blinded Sputum Culture Including Collection of Samples for Microbiology Test.

### Study-specific Materials

The investigator will be provided with the following supplies:

- IB and IB Addendum
- Pharmacy manual/study intervention and procedures manual
- Laboratory manual
- Procedure for Confirmation and Reporting of Results of Blinded Sputum Culture, Including Collection of Samples for Microbiology Test
- PRO questionnaires and PRO completion guidelines
- eCRF completion guidelines
- ICF
- Protocol Supplementary Information

## 8.1. Efficacy Assessments

Microbiology assessments (MAC-LD Treatment Outcome), clinical assessments in MAC-LD, percentage of participants who undergo a change in their MAC-LD treatment regimen, and a lung function assessment using a spirometry test, will be performed in this study.

### 8.1.1. Microbiology Assessments (MAC-LD Treatment Outcome)

Sputum sample will be collected at the timepoints shown in Section 1.3, [Schedule of Activities \(SoA\)](#). Instructions for the collection, handling, storage, and shipment of samples for microbiological assessment can be found in the Procedure for Confirmation and Reporting of Results of Blinded Sputum Culture, Including Collection of Samples for Microbiology Test. All sample collection and processing will be performed according to the approved operating procedures.

#### *Qualitative Culture for MAC (Mycobacteria Growth Indicator Tube [MGIT])*

This is to assess participants' response to treatment by measuring the microbiological response (culture positive or negative) using liquid medium in MGIT. In addition, time to sputum culture conversion and time to positivity are calculated for MGIT.

#### *Qualitative Culture for MAC (7H10 or 7H11 Agar Media)*

This is to assess participants' response to treatment by measuring the microbiological response (culture positive or negative) using 7H10 or 7H11 agar media.

#### *Identification and Speciation Of MAC*

This is for identification and speciation of MAC by matrix-assisted laser desorption ionization time of flight mass spectrometry (MALDI-TOF MS) for MAC from MGIT, 7H10 or 7H11 agar, and positive sputum cultures.

#### *Resistance Determinations*

This is to determine susceptibility of MAC isolates to BDQ, CAM, EB, rifamycins, and other NTM drugs (if possible) by DST using the broth-based microdilution method according to the Clinical and Laboratory Standards Institute [CLSI] M24 guidelines.

#### *Genotyping or Fingerprinting of Isolates*

This is to assess if baseline and postbaseline isolates are the same or different in case of resistance occurring at postbaseline and in case cultures become positive after having been negative, genotyping using variable number tandem repeat (VNTR) or whole genome sequencing (WGS) will be performed.

### 8.1.2. Clinical Assessments in MAC-LD

#### *SGRQ*

CCI

[REDACTED]

Paper-based SGRQ will be provided by the sponsor. It will be recommended that the paper questionnaire be received from the investigator or study staff at the site visit indicated in Section 1.3, [Schedule of Activities \(SoA\)](#) and that subject perform a self-assessment in a waiting room, etc. in an environment where the subject can be instructed on the contents including the assessment period of the questionnaire. It will be allowed that the investigator may also complete the assessment by interviewing (read out each question as written) and obtain the answers from the subject, if the investigator judges that the subject's understanding of the questionnaire including the assessment period is insufficient, etc.

The SGRQ author instructs in the SGRQ manual that “Do not allow patients to take the SGRQ home to be completed since the sponsor cannot be sure that it will be completed without the help of family or friends”.

#### ***QOL-B and NTM module***

CCI [REDACTED]

Paper based QOL-B and NTM module will be provided by the sponsor. It will be recommended that the paper questionnaire be received from the investigator or study staff at the site visit indicated in Section 1.3, [Schedule of Activities \(SoA\)](#) and that subject perform a self-assessment in a waiting room, etc. in an environment where the subject can be instructed on the contents including the assessment period of the questionnaire. It will be allowed that the investigator may also complete the assessment by interviewing (read out each question as written) and obtain the answers from the subject, if the investigator judges that the subject's understanding of the questionnaire including the assessment period is insufficient, etc.

#### ***Percentage of participants who undergo a change in their MAC-LD treatment regimen***

This is to calculate the percentage of participants who have changed to an individualized treatment regimen as defined by SOC of local guidelines or protocol (Section 6.8.1) in both groups and participants who have switched to BDQ-containing regimen in Group B.

***Lung function assessment***

The lung function parameters including forced expiratory volume in one second, forced vital capacity, inspiratory capacity, functional residual capacity, and total lung capacity, will be assessed.

***Change from baseline in chest CT findings***

The change from baseline in chest CT findings (improved, no change, or worsened) will be assessed and their respective percentages will be calculated. The investigators will evaluate comprehensively based on the spread of opacities, number/size of cavitary opacities, degree of bronchiectasis, etc.

**8.2. Safety Assessments**

Safety and tolerability will be evaluated throughout the study from signing of the ICF onwards until the last study-related activity (end of study/early withdrawal).

An IDMC will be established for this study to monitor the safety of participants. Details regarding the IDMC are provided in Committees Structure in Section 10.3, [Appendix 3: Regulatory, Ethical, and Study Oversight Considerations](#).

Adverse events will be reported and followed by the investigator as specified in Section 8.3, [Adverse Events, Serious Adverse Events, and Other Safety Reporting](#) and Section 10.4, [Appendix 4: Adverse Events, Serious Adverse Events, Product Quality Complaints, and Other Safety Reporting: Definitions and Procedures for Recording, Evaluating, Follow-up, and Reporting](#).

Any clinically relevant changes occurring during the study must be recorded on the Adverse Event section of the eCRF.

Any clinically significant abnormalities persisting at the end of the study/early discontinuation visit will be followed by the investigator until resolution or until a clinically stable condition is reached.

The study will include the following evaluations of safety and tolerability according to the time points provided in Section 1.3, [Schedule of Activities \(SoA\)](#).

**8.2.1. Physical Examinations**

Physical examination of all body systems (including height and body weight measurement) and observation for skin events/reactions will be performed before the intake of BDQ and blood sampling at site visit indicated in Section 1.3, [Schedule of Activities \(SoA\)](#). Height will be measured at only screening.

**8.2.2. Vital Signs**

Body temperature (axillary), heart rate, respiratory rate, oxygen saturation, blood pressure (systolic and diastolic) will be assessed, preferably with same position and methodology throughout the study.

Blood pressure and heart rate measurements will be assessed supine or sedentary with a completely automated device. Manual techniques will be used only if an automated device is not available.

Blood pressure and heart rate measurements should be preceded by at least 5 minutes of rest in a quiet setting without distractions (eg, television, cell phones).

### **8.2.3. Electrocardiograms**

During the collection of ECGs, participants should be in a quiet setting without distractions (eg, television, cell phones). Participants should rest in a supine or sedentary position for at least 5 minutes before ECG collection and should refrain from talking or moving arms or legs. If blood sampling or vital sign measurement is scheduled for the same time point as ECG recording, the procedures should be performed in the following order: vital signs, ECG(s), blood draw.

At each time point at which triplicate ECGs are required, 3 individual ECG tracings should be obtained as closely as possible in succession, but no more than 2 minutes apart. The full set of triplicates should be completed within 5 minutes and must be of good quality (stable baseline, free of interference and artefact). ECGs will be recorded at a paper speed of 25 mm per second until 4 regular consecutive complexes are available. If the record is unclear due to the noise, ECGs will be repeated after 1 or 2 minutes, and the clearer recording will be adopted as an original recording. In principle, 2 original ECG recordings will be provided. One original recording will be stored at the study site and another will be sent to a central cardiologist designated by the sponsor for review. Submission of ECG to a central cardiologist will be done by transmission or send a hardcopy ECG if transmission is not possible for any reasons (refer ECG manual for details). The ECG machine dedicated for this study must be used. All tracings will be transmitted for blinded central analysis. Participants found to have a QTcF  $\geq 500$  ms or an increase from baseline (mean of triplicates on Day 1) of  $>60$  ms on ECG at any point during the treatment period will be further investigated. The ECG should be repeated and if confirmed, the investigator should attempt to identify the cause, including checking and correcting abnormal  $K^+$ ,  $Ca^{+2}$ , and  $Mg^{+2}$ . If the participant is taking any drugs suspected of causing QT prolongation, they should be withheld, and the tests repeated after sufficiently long washout to try to identify the cause. Any QTcF prolongation to  $\geq 500$  ms or an increase from baseline (mean of triplicates on Day 1) of  $>60$  ms while on study intervention is considered a notable event and should be reported immediately to the sponsor.

Extra visits will be required for participants meeting certain grading thresholds for changes in QTcF. Additional unscheduled ECG evaluations may be made at the discretion of the investigator.

### **QTcF Prolongation**

If a single ECG shows QTcF  $\geq 500$  ms or an increase from baseline (mean of triplicates on Day 1) of  $>60$  ms, then complete additional triplicate ECGs, evaluate the mean QTcF, and record results on an unscheduled visit form.

If triplicate ECGs confirm a mean QTcF  $\geq 500$  ms or an increase from baseline of  $>60$  ms, the following will be done:

- the investigator must assess potential causes of the abnormality including at a minimum a check and correction of electrolyte imbalances ( $K^+$ ,  $Mg^{+2}$ ,  $Ca^{+2}$ ), review and adjust combination medications as necessary (eg, temporarily discontinuation of BDQ and CAM), and obtain weekly duplicate/triplicate ECGs until resolution,
- if after 2 weeks mean QTcF is  $\geq 500$  ms or increase from baseline of  $>60$  ms, the investigator must permanently stop the study intervention, and continue weekly triplicate ECGs until resolution.

Weekly triplicate ECG monitoring for participants who have recovered from QTcF  $\geq 500$  ms or increase from baseline of  $>60$  ms may be discontinued if over 3 consecutive weeks the triplicate ECGs demonstrate a mean QTcF  $<500$  ms or one time increase of  $\leq 60$  ms. Participants who meet these criteria can be switched to less frequent ECG monitoring per Section 1.3, [Schedule of Activities \(SoA\)](#). If mean QTcF  $<500$  ms or increase of  $\leq 60$  ms is not demonstrated, then weekly triplicate ECGs will be continued at least until the end of the last dose of BDQ plus 4 weeks due to the long half-life of BDQ. At that point, if mean QTcF  $<500$  ms or increase of  $\leq 60$  ms is demonstrated, weekly triplicate ECGs can be switched to less frequent ECG monitoring per Section 1.3, [Schedule of Activities \(SoA\)](#). Otherwise if mean QTcF  $<500$  ms or increase of  $\leq 60$  ms is not demonstrated, the investigator judges whether weekly triplicate ECGs will be continued or be switched to less frequent ECG monitoring per Section 1.3, [Schedule of Activities \(SoA\)](#).

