In South Korea, "KOREAN GUIDELINE FOR TUBERCULOSIS 4th EDITION" is published in 2020, and in Taiwan, "Consensus Statement of Nontuberculous Mycobacterial Lung Disease in Taiwan" is published in 2020. Both diagnostic criteria for NTM-LD and chemotherapy for MAC-LD in both countries are in accordance with an official ATS/IDSA statement, and chemotherapy mainly with 3 drugs consisted of macrolide (CAM or AZM), rifamycin (RFP or RBT), and EB, is recommended as the standard therapy.

In addition, the inclusion of RBT or RFP, a moderate or strong inducer of hepatic cytochrome P450 (CYP) 3A4 enzymes, in the MAC-LD treatment regimen complicates the administration of other important drugs to treat underlying conditions in patients with MAC-LD.

For the most comprehensive nonclinical and clinical information regarding BDQ, refer to the latest version of the Investigator's Brochure (IB) addendum, and local package insert of SIRTURO (BDQ).

The term “study drug” throughout the protocol refers to BDQ. The term “study intervention” throughout the protocol refers to BDQ and rifamycin (RFP or RBT) as defined in Section 6.1, [Study Interventions Administered](#).

The term "sponsor" used throughout this document refers to the entities listed in the Protocol Supplementary Information, which will be provided as a separate document.

The term "participant" throughout the protocol refers to the common term "subject".

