### 2.3.1. Risks for Study Participation

Potential Risks of Clinical Significance	Summary of Data/ Rationale for Risk	Mitigation Strategy
Benefit of BDQ-containing regimen regarding the clinical course of MAC-LD might not be shown.	Clinical efficacy of BDQ in treatment-refractory MAC-LD patients has not been evaluated in human clinical study yet and efficacy is not demonstrated.	
 
A futility analysis will be implemented to evaluate early the benefit/risk balance by assessing safety and efficacy in the first 60 participants (about 30 participants from both groups) to minimize the number of exposure participants in case benefit/risk balance are unfavorable.
 
Unblinding IDMC review will be implemented.
 
Investigator can switch to individual regimen based on the result of non-conversion and clinical worsening.
 

Participants who are randomized to treatment Group B need to continue SOC by Week 24 regardless of the low culture conversion rates.	Based on the result of clinical study in AMK liposome inhalation suspension (ALIS, Arikayce®), culture conversion rate in SOC were about 10%. 	
 
Non-converter in treatment Group B will be assigned to optional cohort to receive the BDQ containing regimen.
 
Investigator can switch to individual regimen based on the result of based on non-conversion and clinical worsening.
 

Risks Due to Study Intervention (BDQ and RFP/RBT) and Combination Drugs (CAM and EB)		
QT prolongation due to administration of BDQ and/or CAM	QT prolongation was identified as known risk and has been observed in nonclinical and clinical studies in MDR-TB patients (see IB  ).	
 
Triplicate ECG will be assessed and monitored by IDMC frequently.
 
Discontinuation of study intervention and combination drugs will be required based on the result of ECG.
 

Risks Due to Study Procedures		

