## 7. DISCONTINUATION OF STUDY INTERVENTION AND PARTICIPANT DISCONTINUATION/WITHDRAWAL

### 7.1. Discontinuation of Study Intervention

A participant's study intervention must be discontinued if:

- The participant withdraws consent to receive study intervention.
- The investigator believes that for safety reasons or tolerability reasons (eg, AE) it is in the best interest of the participant to discontinue study intervention.

- The participant has a QTcF prolongation (defined as a QTcF value  $\geq 500$  ms, or an increase from baseline of  $>60$  ms) at any given time point (confirmed by repeat ECGs).
- The participant requires treatment with any of the prohibited medications listed in Section 6.8, [Concomitant Therapy](#).
- The participant becomes pregnant. Refer to Section 10.5, [Appendix 5: Contraceptive Guidance](#).
- Noncompliance with study intervention administration as defined in [Table 3](#).
- The participants discontinued administration of study intervention before Week 48 in Group A, Week 60 in Group B or OPW48 in optional cohort.

If a participant discontinues study intervention before Week 48 in Group A, Week 60 in Group B or OPW48 in the optional cohort, the participant will receive the assessments of early discontinuation or withdrawal.

The early discontinuation visit assessment will be performed within 7 days of the investigator's discretion to discontinue treatment with study intervention, unless the participant withdraws consent. Study intervention assigned to the participant who discontinued study intervention may not be assigned to another participant.

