##### ***AST and/or ALT Elevation***

$<5.0 \times$  ULN AST or ALT elevation with normal bilirubin:

Participants may continue to take the study intervention. Participants should be followed until resolution (return to baseline) or stabilization of AST/ALT elevation. Clinical symptoms, AST,

ALT, and serum bilirubin should be monitored every 2 weeks until clinically stable as necessary to manage the participant's condition.

$\geq 5.0 \times \text{ULN}$  but  $\leq 8.0 \times \text{ULN}$  AST or ALT elevation or  $\geq 3 \text{ ULN}$  accompanied by bilirubin  $\geq 2.0 \times \text{ULN}$ :

Participants will be permanently discontinued from treatment of the suspected causative background agent or temporarily withhold study intervention at the investigator's discretion. Clinical symptoms, AST, ALT, and serum bilirubin should be monitored every 2 weeks until clinically stable as necessary to manage the participant's condition. If ALT, AST, and bilirubin do not improve or worsens within 2 weeks, the study intervention will be temporarily withheld for up to 2 weeks per investigator discretion. Additional tests should be performed to evaluate the cause of hepatitis (eg, hepatitis A, B, C). Liver enzymes, including serum bilirubin should be monitored as frequently as necessary to manage the participant's condition. If AST/ALT decreases to  $< 5.0 \times \text{ULN}$ , study intervention can be restarted once. Participants who fail to show improvement, demonstrated by no improvement in clinical course or persistent AST and ALT  $\geq 5.0 \times \text{ULN}$  values, or persistent AST/ALT  $\geq 3.0 \times \text{ULN}$  accompanied by bilirubin  $\geq 2.0 \times \text{ULN}$  (over 4 weeks) will have to permanently discontinue the study intervention. Participants should be followed until resolution or stabilization (return to baseline) of AST/ALT/bilirubin elevation.

$> 8.0 \times \text{ULN}$  AST or ALT elevation

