#### **Cardiac Rhythm Disturbances**

The following text describes the minimum requirements for the management of cardiac rhythm disturbances; however, additional management decisions are at the investigator's discretion.

Grade 1 (asymptomatic) or Grade 2 (asymptomatic, transient rhythm abnormality not requiring any treatment) cardiac rhythm disturbances:

Participants may continue to take the study intervention and should be carefully evaluated and followed closely.

Grade 3 (recurrent, persistent, symptomatic arrhythmia requiring treatment) or Grade 4 (unstable dysrhythmia requiring hospitalization and treatment) cardiac rhythm disturbances:

Participants will permanently discontinue the study intervention. QTcF prolongation that results in discontinuation of the study intervention will be reported as AE term of "QT prolonged" of

Grade 2 if no symptoms are present. If symptomatic, then a higher grade may be reported as per the definitions above.

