#### 5. STATISTICAL ANALYSES

##### 5.1. General Considerations

The SAP will use throughout the document the following definition

- Study intervention refers to: Bedaquiline or rifamycin
- Study intervention arm refers to:
  - Group A: BDQ + CAM + EB
  - Group B: rifamycin (RFP or RBT) + CAM + EB

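### The compulsory QTcF stop covers bedaquiline or rifamycin but not clarithromycin, which Section 2.3.1 names as a QT risk, so in Group B it acts on the wrong drug

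*Protocol*

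**What the plan says.** **Definition.** Protocol Section 2 says that the term study intervention "throughout the protocol refers to BDQ and rifamycin (RFP or RBT) as defined in Section 6.1". SAP Section 5.1 agrees: "Study intervention refers to: Bedaquiline or rifamycin". Table 2 in Protocol Section 6.1 lists CAM and ethambutol (EB) separately, as combination drugs given in both groups.

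**Stated risk.** The table in Section 2.3.1 describes the hazard as "QT prolongation due to administration of BDQ and/or CAM". Its mitigation column says: "Discontinuation of study intervention and combination drugs will be required based on the result of ECG".

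**Operative rules.** Section 7.1 opens its list with "A participant's study intervention must be discontinued if" and includes a QTcF of at least 500 ms, or a rise of more than 60 ms from baseline, confirmed on repeat ECG. Section 8.2.3 applies the same thresholds in two steps. The first bullet requires a search for causes and a review of combination medication, with a temporary stop of BDQ and CAM given as an example. The second bullet applies if the prolongation is still present after two weeks: "the investigator must permanently stop the study intervention, and continue weekly triplicate ECGs until resolution". Section 7.1.2 refers back to Section 8.2.3 and adds nothing.

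**Reporting.** Under Cardiac Rhythm Disturbances in Section 8.2.6, the trigger uses the same term: "QTcF prolongation that results in discontinuation of the study intervention will be reported as AE term of" QT prolonged.

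**The concern.** The compulsory step is written in terms of a drug class that excludes one of the two drugs the protocol itself holds responsible for QT prolongation. In Group B the mismatch is complete. The only named QT-risk drug those participants take is CAM, and the rule orders rifamycin to be stopped. An investigator who follows Section 8.2.3 to the letter and one who follows Section 2.3.1 would do different things.

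What is at stake is the clarity of a cardiac safety rule at the point where discretion ends. The reporting of QT-related stops is also affected, because the sentence in Section 8.2.6 is triggered only when study intervention is discontinued.

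**Working it through.** No plan figure needs reproducing. The check substitutes the definition into each rule and compares the result with Section 2.3.1.

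**1. Can the term be read loosely to include CAM?** No. Section 6.8, in its list of drugs prohibited for QT reasons, names study interventions and combination drugs side by side when both are meant. Section 6.8.1 lists stopping study intervention and stopping CAM as separate events. The liver rule in Section 8.2.6 also keeps the classes apart, with participants being "permanently discontinued from treatment of the suspected causative background agent or temporarily withhold study intervention". So the protocol can reach a background drug when it intends to.

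**2. Substitution by group.**

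| Group | Drugs taken | Named as QT risk in 2.3.1 | Removed by the compulsory stop | Named drugs reached |
|---|---|---|---|---|
| A | BDQ, CAM, EB | BDQ, CAM | BDQ | 1 of 2 |
| Optional cohort | BDQ, CAM, EB | BDQ, CAM | BDQ | 1 of 2 |
| B, before any switch | rifamycin, CAM, EB | CAM | rifamycin | 0 of 1 |

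**3. How strong is each stop?** Section 7.1 says must be discontinued. Only the second bullet of Section 8.2.3 says permanently. Section 2.3.1 says discontinuation will be required, and gives neither a threshold nor a duration.

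**4. What else in the protocol reaches CAM?**
- Section 8.2.3, main text: drugs suspected of causing QT prolongation should be withheld and the ECG repeated after washout. CAM fits this description, but the aim is to find the cause and the wording is advisory.
- Section 8.2.3, first bullet: review of combination drugs is required. The adjustment is as necessary, and stopping CAM is a temporary example.
- Section 6.8.1: if a regimen outside the list is judged necessary, for instance because study intervention stops, the participant leaves the study for a site regimen. All 3 Group A and all 3 Group B individualized regimens (6 of 6) contain both the study intervention and CAM, so stopping either takes the participant off every listed option. Nothing is said about CAM in the site regimen.
- Section 7.2: stopping study intervention does not by itself mean withdrawal from the study.

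None of these makes stopping CAM compulsory once prolongation persists at two weeks.

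**5. Primary endpoint.** SAP Section 5.3.2 already counts treatment discontinuation before Week 24 as nonconversion. A participant who reaches the stop before Week 24 is a nonconverter whether or not CAM is named.

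**The case against.** The best defence is that Section 2.3.1 is one row of a risk table and summarises Section 8.2.3 as a whole: withhold suspect drugs, review and adjust combination drugs, then stop study intervention for good. On that reading there is little conflict. Section 6.4 also leaves interruption of combination drugs to investigators under local practice and labelling, which suggests deliberate delegation for a locally sourced product. Nothing tells sites to resume CAM; the restart instructions in Table 3 concern BDQ. Each event goes to the sponsor at once, and the data monitoring committee includes a cardiologist.

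Much of this stands. It shows that CAM is not ignored, and that an attentive investigator would probably have withheld it before the two-week point. It does not explain why the compulsory step in Group B falls on rifamycin, and it does not turn advisory wording into a requirement.

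Three stronger readings are tempting but not supported:
- That Sections 7.1 and 8.2.3 both set a permanent stop. Only Section 8.2.3 does.
- That Section 2.3.1 demands permanent removal of every combination drug, EB included. It sets no duration, and EB is not named as a QT risk.
- That continuing CAM after BDQ stops is shown to worsen QT. Section 2.2 reports that CAM raised BDQ AUC by 12% to 14% and lowered AUC of its metabolite M2 by 42% to 51%. The net QT effect is not established.

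**Conclusion.** The concern holds as a low-severity correction to a safety rule. The compulsory QTcF stop reaches one of two named QT-risk drugs in Group A and the optional cohort, and none of one in Group B, where it acts on a drug not listed as a QT risk. These counts describe the coverage of the wording; they do not measure harm. The documents give no QTcF event rate, so no number of affected participants can be derived. The rule applies to all 62 planned participants per group, but that is its scope and not an expected count.

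The conclusion rests on reading study intervention as the protocol defines it and on taking Section 2.3.1 at its word about which drugs carry the risk. A reader might infer that participants are left on CAM unprotected, or that efficacy results are at risk. The withholding and review steps in Section 8.2.3 and the usual exit under Section 6.8.1 argue against the first, and the nonconverter rule argues against the second. The documents do not say whether dosing is complete. If it is, the remaining value lies in how QT-related stops are reported.

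**What to change.** - In the QTcF bullet of Section 7.1 and the second bullet of Section 8.2.3, name CAM with the study intervention: BDQ and CAM in Group A and the optional cohort; CAM in Group B, with the participant leaving assigned treatment under Section 6.8.1.
- State that CAM withheld under the earlier steps of Section 8.2.3 is not resumed within the study.
- In Section 2.3.1, replace combination drugs with CAM, so that the sections agree and an EB stop is not implied.
- Align the QT reporting sentence in Section 8.2.6, so that a QT-related CAM stop is captured.

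Simply softening Section 2.3.1 to match Section 8.2.3 would remove the contradiction but leave the Group B stop pointing at rifamycin.

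The cost is wording in four sections and a letter to sites. The clinical downside is that a participant who meets the stop criterion loses protocol CAM, a cornerstone of treatment according to Section 2, even where another cause is suspected. Section 2.3.1 already implies this. Sample size, primary endpoint and SAP analyses are unchanged.
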